## 3. OBJECTIVES AND ENDPOINTS

**Table 5: Objectives and Endpoints (Outcome Measures)**

OBJECTIVES	ENDPOINTS (OUTCOME MEASURES)
Primary	

 
To evaluate the safety and reactogenicity of a 2-dose vaccination schedule of mRNA-1273, given 28 days apart, across 5 dosages in healthy adults.
 
	
 
Frequency and grade of each solicited local and systemic reactogenicity AE during a 7-day follow-up period post each vaccination.
 
Frequency and grade of any unsolicited AEs during the 28-day follow-up period post each vaccination.
 
Frequency of any SAEs, Protocol Specified AESIs, NOCMCs, and MAAEs from Day 1 to Day 394.
 

Secondary	

 
To evaluate the immunogenicity as measured by IgG ELISA to the SARS-CoV-2 S (spike) protein following a 2-dose vaccination schedule of mRNA-1273 at Day 57.
 
	
 
GMT of antibody at Day 57.
 
Percentage of subjects who seroconverted, defined as a 4-fold change in antibody titer from baseline.
 
The GMFR in IgG titer from baseline.
 

Exploratory	

OBJECTIVES	ENDPOINTS (OUTCOME MEASURES)

 
To evaluate the immunogenicity as measured by IgG ELISA to the SARS-CoV-2 S (spike) protein following a 2-dose vaccination schedule of mRNA-1273 at all timepoints, other than Day 57.
 
	
 
GMT of antibody at each timepoint.
 
Percentage of subjects who seroconverted at each timepoint.
 
The GMFR in IgG titer from baseline at each post-vaccination timepoint.
 

 
To evaluate the immunogenicity as measured by IgM and IgA ELISA to the SARS-CoV-2 S (spike) protein following a 2-dose vaccination schedule of mRNA-1273 given 28 days apart.
 
	
 
GMT at each timepoint.
 
Percentage of subjects who seroconverted at each timepoint.
 
The GMFR in IgM and IgA titer from baseline at each post-vaccination timepoint.
 

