- Reactogenicity assessments of solicited AEs occurring from the time of each vaccination through 7 days post each vaccination, will include an assessment of injection site reactions—erythema, edema/induration and pain, as well as systemic reactions—fever, fatigue, chills, myalgia (exclusive of the injection site), arthralgia, headache, and nausea. Pre-administration reactogenicity assessments will be performed immediately prior to each vaccination to establish baseline, then the vaccination will be given.
- Subjects will be observed in the clinic for at least 60 minutes post each vaccination. The vaccination site will be examined, post-administration reactogenicity assessments will be performed, and any AEs/SAEs will be recorded on the appropriate DCF prior to discharge from the clinic. The vaccination site will also be examined on Days 8 and 36.
- Vital signs: Vital sign measurements will include systolic and diastolic BP, HR, and oral temperature. Vital signs will be measured at timepoints specified in the SOA. On Days 1 and 29, vital sign measurements will be collected prior to vaccine administration. Vital signs assessed on Day 1 prior to the first vaccination will be considered as baseline. Subjects must not eat or drink anything hot or cold within 10 minutes prior to taking oral temperature.
- Clinical laboratory evaluations:
  - Fasting is not required before collection of clinical laboratory evaluations.
  - Serum pregnancy test will be performed locally by the site laboratory at the screening visit, and urine or serum pregnancy test will be performed locally by the site laboratory within 24 hours prior to each vaccination on Days 1 and 29, and as needed at interim or unscheduled visits for all women of childbearing potential. Results must be confirmed as negative prior to enrollment on Day 1 and administration of each vaccination.
  - Serology: hepatitis B surface antigen, hepatitis C virus antibody, and HIV types 1 and 2 antigen/antibody at the screening visit only.
  - Urine drug screen for drugs of abuse (components per the standard panel at the site laboratory) at the screening visit only.
  - Clinical screening laboratory evaluations (WBCs, Hgb, PLTs, ALT, AST, ALP, T. Bili, Cr, Lipase, PT, and PTT) will be collected at the screening visit.

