## **8.3 Adverse Events and Serious Adverse Events**

### **8.3.1 Definition of Adverse Event (AE)**

AE means any untoward medical occurrence associated with the use of an intervention in humans, whether or not considered intervention-related (21 CFR 312.32 (a)). An AE can therefore be any unfavorable and unintended sign (including an abnormal clinical laboratory finding), symptom or disease temporally associated with the use of medicinal (investigational) product.

Any medical condition that is present at the time that the subject is screened will be considered as baseline and not reported as an AE. However, if the severity of any pre-existing medical condition increases, it should be recorded as an AE.

AEs can be further divided into solicited AEs and unsolicited AEs. Solicited AEs are those for which the study team will specifically query the subject whether they occurred. Unsolicited AEs are those events that the subject report occurring without being queried about the specific event.

All AEs will be assessed for severity and relationship to study intervention ([Section 8.3.3](#)). Reporting of all AEs, solicited and unsolicited, will occur during the period from study product administration on Day 1 through 28 days after the second vaccination. After Day 57 through the end of study on Day 394, only SAEs, Protocol Specified AESIs, MAAEs, and NOCMCs will be reported as AEs.

All AEs, solicited and unsolicited, will be captured on the appropriate DCF. Information to be collected for AEs includes event description, date of onset, assessment of severity, relationship to study product and alternate etiology (assessed only by those with the training and authority to make a diagnosis and listed on the Form FDA 1572 as the participating site PI or appropriate sub-investigator), date of resolution, seriousness, and outcome. AEs occurring during the study-collection and reporting period will be documented appropriately regardless of relationship.

AEs will be followed to resolution or stabilization.

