### 9.4.4 Safety Analyses

Summaries and analysis of safety data will be presented for the Safety Analysis Population.

Solicited AEs will be summarized by severity for each day post vaccination (Days 1-8) and as the maximum severity over all 8 days. Additionally, solicited AEs will be analyzed by taking the most severe response over the follow-up period, dichotomizing into a binary variable (none versus mild, moderate, or severe) and using standard techniques, such as exact confidence

intervals (CI), to summarize the proportion of subjects reporting each symptom, any application site symptom, and any systemic symptom.

Unsolicited non-serious AEs will be collected from the time of first vaccination through 28 days after the second vaccination. Unsolicited AEs will be coded by MedDRA for preferred term and system organ class (SOC). SAEs, Protocol Specified AESIs, MAAEs, and NOCMCs will be collected from the time of first vaccination through the end of the study (Day 394). The numbers of SAEs and MAAEs will be reported by detailed listings showing the event description, MedDRA preferred term and SOC, relevant dates (vaccinations and AEs), severity, relatedness, and outcome for each event. Non-serious unsolicited AEs will be summarized as number and percentage of subjects reporting at least one event in each MedDRA preferred term and SOC, cross tabulated by severity and relationship to study product. Additionally, the proportion of subjects and exact 95% CIs of AEs in aggregate and by MedDRA categories will be computed.

Clinical laboratory data will be summarized by severity for each visit, and as the maximum over all post-vaccination visits. Graphical presentations may include box plots and shift plots.

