9.3.1. Solicited Events and Symptoms

Systemic solicited adverse events were collected pre-vaccination, and systemic and local solicited adverse events were collected 30 minutes post-vaccination and then daily for 7 days after each vaccination and graded on a scale of 0 (absent), 1 (mild), 2 (moderate) and 3 (severe). Systemic events include: fatigue, headache, myalgia, arthralgia, nausea, chills and fever. Local events include: pain at injection site, erythema, and induration.

The proportion of subjects reporting at least one solicited adverse event will be summarized for each solicited adverse event, any systemic symptom, any local symptom, and any symptoms. The 95% CI calculated using Clopper-Pearson methodology from a binomial distribution (SAS Proc Freq with a binomial option) will be presented (Table 144, Table 145, and Table 146).

For each systemic and local event, any systemic event, any local event, and any solicited event, the maximum severity over 7 days after each vaccination will be summarized for the Safety population. The number and percentage of subjects reporting each event will be summarized by the maximum severity and treatment group, separately for each vaccination and over all vaccinations (Table 147, Table 148, Table 149, Table 150, Table 151, and Table 152). For each event the denominator is the number of subjects with non-missing data for the specific event.

The number of subjects reporting a solicited adverse event will be summarized for each day post vaccination for each vaccination and for all vaccinations combined both in a summary table starting at Table 153 and ending at Table 212 and graphically in a bar chart (Figure 122, Figure 123, Figure 124, Figure 125, Figure 126, and Figure 127).

The mean, standard deviation, median, minimum and maximum duration of solicited events will be summarized (Table 213, Table 214, Table 215).

Day of solicited symptom onset will be summarized graphically (starting at Figure 128 and ending at Figure 139).

Solicited adverse events by subject will be presented in listings (Listing 10 and Listing 11) and graphically (starting at Figure 140 and ending at Figure 175).

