14.3.1.1 Solicited Adverse Events

Table 144: Number and Percentage of Subjects Experiencing Solicited Events by Symptom, Maximum Severity, Dose, and Treatment Group - Any Symptom - 18-55 Years of Age*

Symptom	Dose	Severity	25 µg mRNA-1273 (N=X)		50 µg mRNA -1273 (N=X)		100 µg mRNA -1273 (N=X)		250 µg mRNA -1273 (N=X)		All Subjects (N=X)	
			n	%	n	%	n	%	n	%	n	%
Any Symptom	Dose 1	None										
		Mild										
		Moderate										
		Severe										
	Dose 2	None										
		Mild										
		Moderate										
		Severe										
	Any Dose	None										
		Mild										
		Moderate										
		Severe										

Severity is the maximum severity reported over all solicited symptoms post dosing for each subject.
N=All subjects receiving Dose 1 with any solicited event data recorded in the database.

Tables with Similar Format:

Table 145: Number and Percentage of Subjects Experiencing Solicited Events by Symptom, Maximum Severity, Dose, and Treatment Group - Any Symptom – 56-70 Years of Age*

Table 146: Number and Percentage of Subjects Experiencing Solicited Events by Symptom, Maximum Severity, Dose, and Treatment Group - Any Symptom - ≥71 Years of Age*

Table 147: Number and Percentage of Subjects Experiencing Solicited Events by Symptom, Maximum Severity, Dose, and Treatment Group - Systemic Symptoms - 18-55 Years of Age*

			25 µg mRNA-1273 (N=X)		50 µg mRNA -1273 (N=X)		100 µg mRNA -1273 (N=X)		250 µg mRNA -1273 (N=X)		All Subjects (N=X)	
Symptom	Dose	Severity	n	%	n	%	n	%	n	%	n	%
Any Systemic Symptom	Dose 1	None										
		Mild										
		Moderate										
		Severe										
	Dose 2	None										
		Mild										
		Moderate										
		Severe										
	Any Dose	None										
		Mild										
		Moderate										
		Severe										
Arthralgia	Dose 1	None										
		Mild										
		Moderate										
		Severe										
	Dose 2	None										
		Mild										
		Moderate										
		Severe										

			25 µg mRNA-1273 (N=X)		50 µg mRNA -1273 (N=X)		100 µg mRNA -1273 (N=X)		250 µg mRNA -1273 (N=X)		All Subjects (N=X)	
Symptom	Dose	Severity	n	%	n	%	n	%	n	%	n	%
	Any Dose	None										
		Mild										
		Moderate										
		Severe										
Fatigue	Dose 1	None										
		Mild										
		Moderate										
		Severe										
	Dose 2	None										
		Mild										
		Moderate										
		Severe										
	Any Dose	None										
		Mild										
		Moderate										
		Severe										
Fever ^a	Dose 1	None										
		Mild										

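### Systemic reactogenicity is summarised at its worst post-dose grade with no reference to the subject's own pre-dose grade, although the protocol takes that grade before each dose as a baseline

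*SAP*

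**What the plan says.** Protocol 8.2 gives the purpose of the pre-dose assessment: "Pre-administration reactogenicity assessments will be performed immediately prior to each vaccination to establish baseline, then the vaccination will be given". SAP 9.3.1 confirms that the systemic part exists: "Systemic solicited adverse events were collected pre-vaccination".

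The primary endpoint (Protocol Section 3, Table 5) is "Frequency and grade of each solicited local and systemic reactogenicity AE during a 7-day follow-up period post each vaccination". For its analysis, Protocol 9.4.4 states that "solicited AEs will be analyzed by taking the most severe response over the follow-up period", then splits the result into none versus any grade and reports proportions with exact intervals. SAP Section 9 repeats this. SAP 9.3.1 assigns the proportions to Tables 144–146 and the maximum severity over the 7 days after each dose to Tables 147–152. The footnote to Tables 144, 147 and 150 is "Severity is the maximum severity reported over all solicited symptoms post dosing for each subject".

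The pre-dose grade has its own column in the by-day systemic shells (Tables 153–182). Those tables carry no asterisk, so they are outside the interim clinical study report. Tables 144–152 carry one. SAP 3.2 defines baseline only as the last value before the first vaccination.

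**The concern.** The plan collects a symptom baseline before each dose and then summarises the primary reactogenicity endpoint without it. A systemic symptom that is present before the injection and unchanged afterwards enters Tables 144–149 at its full grade, exactly as a new reaction would.

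This matters more than usual because the trial is open-label with no placebo arm (Protocol 4.2). The tables offer no other within-trial reference for background fatigue, headache, myalgia or arthralgia. Pre-dose symptoms are also possible under the entry rules. Stable chronic conditions are allowed (inclusion criterion 10), a nearly resolved acute illness is allowed (footnote to exclusion criterion 5), and subjects with a minor illness without fever may be vaccinated (Protocol 7.1.3.2). With 10 or 15 subjects per cohort, a single carried-over symptom visibly moves a percentage.

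**Working it through.** **1. What the rule does to an unchanged symptom.** Take a subject with grade 1 arthralgia before Dose 2, grade 1 on the following days, and nothing else.
- Tables 144–149: maximum post-dose grade is 1, so the subject is counted as mild.
- Increase over own pre-dose grade: 1 − 1 = 0, so the subject would not be counted.
- Tables 153–182: the subject adds one to the Pre-Dose column and one to each post-dose day. These are marginal counts, so the table cannot show whether the same subject is in both or whether anyone worsened.

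**2. The plan's own figures.** Protocol 9.2 uses P(at least one) = 1 − (1 − p)^n. This reproduces Table 9:
- n = 15: 53.7%, 79.4% and 96.5% at p = 5%, 10% and 20%
- n = 10: 40.1%, 65.1% and 89.3% at the same rates

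**3. The same formula applied to carry-over.** Let b be the proportion of subjects with a given systemic symptom before a dose that persists after it. The documents give no value, so b is an assumption. For one symptom and one dose:

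| b | Expected subjects, n = 15 | Expected subjects, n = 10 | Chance of at least one, n = 15 | Chance of at least one, n = 10 |
|---|---|---|---|---|
| 2% | 0.3 | 0.2 | 26% | 18% |
| 5% | 0.75 | 0.5 | 54% | 40% |
| 10% | 1.5 | 1.0 | 79% | 65% |
| 20% | 3.0 | 2.0 | 96.5% | 89% |

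One subject is 1/10 = 10 points or 1/15 = 6.7 points.

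**4. Effect on the reported rate.** Let r be the true rate of new or worsened symptoms, independent of b. Then

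reported rate = 1 − (1 − b)(1 − r) = r + b(1 − r), so the inflation is b(1 − r).

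| b | r = 20% | r = 50% | r = 80% |
|---|---|---|---|
| 2% | +1.6 | +1.0 | +0.4 |
| 5% | +4.0 | +2.5 | +1.0 |
| 10% | +8.0 | +5.0 | +2.0 |
| 20% | +16.0 | +10.0 | +4.0 |

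(percentage points)

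**5. Effect on a dose contrast.** If b is the same in both cohorts, a difference in r shrinks by the factor (1 − b). For 30% versus 70% and b = 10%, the reported rates are 0.30 + 0.10 × 0.70 = 37% and 0.70 + 0.10 × 0.30 = 73%. The difference falls from 40 to 36 points.

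**The case against.** The tables do estimate the endpoint as worded. It asks for solicited events in the week after each dose, and the protocol's AE definition does not depend on cause. Counting everything after the dose is the cautious choice in a first-in-human trial. This stands, and it is why the existing rows should remain.

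The pre-dose grade is not ignored altogether. It is displayed in Tables 153–182, and by-subject listings and figures of solicited events are planned. That also stands, but none of the tables gives a within-subject comparison.

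A pre-dose snapshot is an incomplete control, because it cannot remove background symptoms that begin during the following week. Protocol 12.2 cites solicited systemic events in 42.2% and 36.5% of placebo recipients after the first and second injections of the phase 3 trial. The added rows would therefore reduce carry-over without isolating a vaccine effect, so they should supplement the any-post-dose rows and not replace them.

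The size may be small. Subjects are selected for good health, and exclusion criterion 5 screens out acute illness within 72 hours of each vaccination, so a high b has no support in the documents. The intervals are wide in any case: for 3 of 10 the exact 95% interval is 6.7% to 65.2%.

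A reader might infer three further things that the documents do not support:
- **That Protocol 8.3.1 is breached.** It says that "if the severity of any pre-existing medical condition increases, it should be recorded as an AE", but it concerns conditions present at screening, not a symptom graded just before a dose. It supports the idea only by analogy.
- **That the age contrast is flattened.** This needs b to be higher in the older strata, and no passage gives b by age.
- **That local symptoms are affected in the same way.** Protocol 8.2 includes injection-site signs in its reactogenicity assessments and does not limit the pre-dose assessment to systemic symptoms. SAP 9.3.1, however, says: "Systemic solicited adverse events were collected pre-vaccination, and systemic and local solicited adverse events were collected 30 minutes post-vaccination". The absence of a pre-dose column in Tables 183–212 agrees with the SAP, so this is a discrepancy to reconcile and not evidence of unused data.

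**Conclusion.** The point holds for systemic solicited symptoms. Tables 144–149 count an unchanged pre-dose symptom as a post-vaccination reactogenicity event, no tabulation shows who worsened, and no pre-Dose-2 baseline is defined although the assessment is taken. The interim report would carry the unadjusted tables without even the marginal pre-dose column.

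The size cannot be derived from the documents. For b of 5–10% and r of 20–80%, inflation is about 1 to 8 percentage points, assuming that the pre-dose symptom persists and is independent of a true reaction. It shrinks as the true reaction rate rises.

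This is a missing summary, not an invalid analysis. It is worth adding because the systemic data are already collected and there is no placebo arm.

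**What to change.** 1. In SAP 3.2 and 9.3.1, define for each systemic solicited symptom a baseline for each dose: the grade recorded immediately before that vaccination.
2. In Tables 147–149, and for the systemic proportions that SAP 9.3.1 assigns to Tables 144–146, add beside the existing rows the number and percentage, with exact 95% CI, of subjects whose maximum post-dose grade exceeds their own pre-dose grade for that symptom. For the any-systemic row, count a subject when at least one systemic symptom meets this. For the any-dose row, compare each dose with its own baseline. State the denominator as subjects with a pre-dose grade and at least one post-dose grade.
3. Keep the any-post-dose rows, present both, and include the new rows in the interim report.
4. Reconcile Protocol 8.2 with SAP 9.3.1 on whether local symptoms are assessed before each dose, before adding any local pre-dose column.

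For systemic symptoms the cost is SAP wording and extra rows in tables already planned. It needs no added visits, subjects or data collection.

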14.3.1.2 Unsolicited Adverse Events

Table 216: All Adverse Events Cross-Classified by MedDRA® System Organ Class, Severity, and Relationship to Study Treatment, and Treatment Group – 25 µg mRNA-1273 18-55 years (N=X)*

MedDRA System Organ Class	Severity	Relationship to Vaccination		
		Not Related (n)	Related (n)	Not Yet Determined (n)
Any SOC	Mild			
	Moderate			
	Severe			
Blood And Lymphatic System Disorders	Mild			
	Moderate			
	Severe			
Cardiac Disorders	Mild			
	Moderate			
	Severe			
Ear And Labyrinth Disorders	Mild			
	Moderate			
	Severe			
Eye Disorders	Mild			
	Moderate			
	Severe			
Gastrointestinal Disorders	Mild			
	Moderate			
	Severe			
	Mild			

MedDRA System Organ Class	Severity	Relationship to Vaccination		
		Not Related (n)	Related (n)	Not Yet Determined (n)
General Disorders And Administration Site Conditions	Moderate			
	Severe			
Immune System Disorders	Mild			
	Moderate			
	Severe			
Infections And Infestations	Mild			
	Moderate			
	Severe			
Injury, Poisoning And Procedural Complications	Mild			
	Moderate			
	Severe			
Investigations	Mild			
	Moderate			
	Severe			
Metabolism And Nutrition Disorders	Mild			
	Moderate			
	Severe			
Musculoskeletal And Connective Tissue Disorders	Mild			
	Moderate			
	Severe			
Neoplasms Benign, Malignant And Unspecified (Incl Cysts And Polyps)	Mild			
	Moderate			

		Relationship to Vaccination		
MedDRA System Organ Class	Severity	Not Related (n)	Related (n)	Not Yet Determined (n)
	Severe			
Nervous System Disorders	Mild			
	Moderate			
	Severe			
Psychiatric Disorders	Mild			
	Moderate			
	Severe			
Reproductive System And Breast Disorders	Mild			
	Moderate			
	Severe			
Respiratory, Thoracic And Mediastinal Disorders	Mild			
	Moderate			
	Severe			
Skin And Subcutaneous Tissue Disorders	Mild			
	Moderate			
	Severe			
Vascular Disorders	Mild			
	Moderate			
	Severe			
[Repeat for all reported SOC]				

Tables with Similar Format:

- Table 217:** All Adverse Events Cross-Classified by MedDRA® System Organ Class, Severity, and Relationship to Study Treatment, and Treatment Group – 50 µg mRNA-1273 18-55 years (N=X)*
- Table 218:** All Adverse Events Cross-Classified by MedDRA® System Organ Class, Severity, and Relationship to Study Treatment, and Treatment Group – 100 µg mRNA-1273 18-55 years (N=X)*
- Table 219:** All Adverse Events Cross-Classified by MedDRA® System Organ Class, Severity, and Relationship to Study Treatment, and Treatment Group – 250 µg mRNA-1273 18-55 years (N=X)*
- Table 220:** All Adverse Events Cross-Classified by MedDRA® System Organ Class, Severity, and Relationship to Study Treatment, and Treatment Group – All Subjects 18-55 years (N=X)*
- Table 221:** All Adverse Events Cross-Classified by MedDRA® System Organ Class, Severity, and Relationship to Study Treatment, and Treatment Group – 25 µg mRNA-1273 56-70 years (N=X)*
- Table 222:** All Adverse Events Cross-Classified by MedDRA® System Organ Class, Severity, and Relationship to Study Treatment, and Treatment Group – 50 µg mRNA-1273 56-70 years (N=X)*
- Table 223:** All Adverse Events Cross-Classified by MedDRA® System Organ Class, Severity, and Relationship to Study Treatment, and Treatment Group – 100 µg mRNA-1273 56-70 years (N=X)*
- Table 224:** All Adverse Events Cross-Classified by MedDRA® System Organ Class, Severity, and Relationship to Study Treatment, and Treatment Group – All Subjects 56-70 years (N=X)*
- Table 225:** All Adverse Events Cross-Classified by MedDRA® System Organ Class, Severity, and Relationship to Study Treatment, and Treatment Group – 25 µg mRNA-1273 ≥71 years (N=X)*
- Table 226:** All Adverse Events Cross-Classified by MedDRA® System Organ Class, Severity, and Relationship to Study Treatment, and Treatment Group – 50 µg mRNA-1273 ≥71 years (N=X)*
- Table 227:** All Adverse Events Cross-Classified by MedDRA® System Organ Class, Severity, and Relationship to Study Treatment, and Treatment Group – 100 µg mRNA-1273 ≥71 years (N=X)*
- Table 228:** All Adverse Events Cross-Classified by MedDRA® System Organ Class, Severity, and Relationship to Study Treatment, and Treatment Group – All Subjects ≥71 years (N=X)*

Table 229: Summary of All Unsolicited Adverse Events by MedDRA® System Organ Class and Preferred Term, Severity, Relationship, and Treatment Group – 25 µg mRNA-1273 18-55 years (N=X)*

System Organ Class (SOC)	Preferred Term (PT)	Total Events (n)	Severity			Relationship to Study Vaccination		
			Mild (n)	Moderate (n)	Severe (n)	Not Related (n)	Related (n)	Not Yet Determined (n)
Any SOC	Any PT							
Gastrointestinal disorders	Any PT							
	Flatulence							
	Vomiting							
General disorders and administration site conditions	Any PT							
	Fatigue							
	Injection site irritation							
	Vessel puncture site bruise							
Infections and infestations	Any PT							
	Hordeolum							
	Pustule							
Injury, poisoning and procedural complications	Any PT							
	Contusion							
	Muscle strain							
	Skin abrasion							
	Skin laceration							
	Wound							
Musculoskeletal and connective tissue disorders	Any PT							
	Muscular weakness							
	Pain in jaw							

System Organ Class (SOC)	Preferred Term (PT)	Total Events (n)	Severity			Relationship to Study Vaccination		
			Mild (n)	Moderate (n)	Severe (n)	Not Related (n)	Related (n)	Not Yet Determined (n)
Nervous system disorders	Presyncope							
Respiratory, thoracic and mediastinal disorders	Any PT							
	Dyspnoea exertional							
	Oropharyngeal pain							
Skin and subcutaneous tissue disorders	Any PT							
	Dermatitis contact							
	Erythema							
	Petechiae							
	Urticaria							
Vascular disorders	Systolic hypertension							
[Repeat for all reported SOC]	[Repeat for all reported PT]							

Tables with Similar Format:

- Table 230:** Summary of All Unsolicited Adverse Events by MedDRA® System Organ Class and Preferred Term, Severity, Relationship, and Treatment Group – 50 µg mRNA-1273 18-55 years (N=X)*
- Table 231:** Summary of All Unsolicited Adverse Events by MedDRA® System Organ Class and Preferred Term, Severity, Relationship, and Treatment Group – 100 µg mRNA-1273 18-55 years (N=X)*
- Table 232:** Summary of All Unsolicited Adverse Events by MedDRA® System Organ Class and Preferred Term, Severity, Relationship, and Treatment Group – 250 µg mRNA-1273 18-55 years (N=X)*
- Table 233:** Summary of All Unsolicited Adverse Events by MedDRA® System Organ Class and Preferred Term, Severity, Relationship, and Treatment Group – All Subjects 18-55 years (N=X)*
- Table 234:** Summary of All Unsolicited Adverse Events by MedDRA® System Organ Class and Preferred Term, Severity, Relationship, and Treatment Group – 25 µg mRNA-1273 56-70 years (N=X)*

-
- Table 235:** Summary of All Unsolicited Adverse Events by MedDRA® System Organ Class and Preferred Term, Severity, Relationship, and Treatment Group – 50 µg mRNA-1273 56-70 years (N=X)*
- Table 236:** Summary of All Unsolicited Adverse Events by MedDRA® System Organ Class and Preferred Term, Severity, Relationship, and Treatment Group – 100 µg mRNA-1273 56-70 years (N=X)*
- Table 237:** Summary of All Unsolicited Adverse Events by MedDRA® System Organ Class and Preferred Term, Severity, Relationship, and Treatment Group – All Subjects 56-70 years (N=X)*
- Table 238:** Summary of All Unsolicited Adverse Events by MedDRA® System Organ Class and Preferred Term, Severity, Relationship, and Treatment Group – 25 µg mRNA-1273 ≥71 years (N=X)*
- Table 239:** Summary of All Unsolicited Adverse Events by MedDRA® System Organ Class and Preferred Term, Severity, Relationship, and Treatment Group – 50 µg mRNA-1273 ≥71 years (N=X)*
- Table 240:** Summary of All Unsolicited Adverse Events by MedDRA® System Organ Class and Preferred Term, Severity, Relationship, and Treatment Group – 100 µg mRNA-1273 ≥71 years (N=X)*
- Table 241:** Summary of All Unsolicited Adverse Events by MedDRA® System Organ Class and Preferred Term, Severity, Relationship, and Treatment Group – All Subjects ≥71 years (N=X)*

Table 242: Number and Percentage of Subjects Experiencing Unsolicited Adverse Events by MedDRA® System Organ Class and Preferred Term, Severity, Relationship, and Treatment Group – 25 µg mRNA-1273 18-55 Years of Age (N=X)*

				Severity						Relationship to Study Vaccination			
		Any Incidence		Mild		Moderate		Severe		Not Related		Related	
MedDRA System Organ Class	MedDRA Preferred Term	n	%	n	%	n	%	n	%	n	%	n	%
Any SOC	Any PT												
Gastrointestinal disorders	Any PT												
	Flatulence												
	Vomiting												
General disorders and administration site conditions	Any PT												
	Fatigue												
	Injection site irritation												
	Vessel puncture site bruise												
Infections and infestations	Any PT												
	Hordeolum												
	Pustule												
Injury, poisoning and procedural complications	Any PT												
	Contusion												
	Muscle strain												
	Skin abrasion												
	Skin laceration												
	Wound												
	Any PT												

				Severity						Relationship to Study Vaccination			
		Any Incidence		Mild		Moderate		Severe		Not Related		Related	
MedDRA System Organ Class	MedDRA Preferred Term	n	%	n	%	n	%	n	%	n	%	n	%
Musculoskeletal and connective tissue disorders	Muscular weakness												
	Pain in jaw												
Nervous system disorders	Presyncope												
Respiratory, thoracic and mediastinal disorders	Any PT												
	Dyspnoea exertional												
	Oropharyngeal pain												
Skin and subcutaneous tissue disorders	Any PT												
	Dermatitis contact												
	Erythema												
	Petechiae												
	Urticaria												
Vascular disorders	Systolic hypertension												
[Repeat for all reported SOC]	[Repeate for all reported PT]												

Note: This table presents number and percentage of subjects. A subject is only counted once per PT and is summarized according to their highest severity and closest relationship.

Tables with Similar Format:

- Table 243:** Number and Percentage of Subjects Experiencing Unsolicited Adverse Events by MedDRA® System Organ Class and Preferred Term, Severity, Relationship, and Treatment Group – 50 µg mRNA-1273 18-55 Years of Age (N=X)*
- Table 244:** Number and Percentage of Subjects Experiencing Unsolicited Adverse Events by MedDRA® System Organ Class and Preferred Term, Severity, Relationship, and Treatment Group – 100 µg mRNA-1273 18-55 Years of Age (N=X)*
- Table 245:** Number and Percentage of Subjects Experiencing Unsolicited Adverse Events by MedDRA® System Organ Class and Preferred Term, Severity, Relationship, and Treatment Group – 250 µg mRNA-1273 18-55 Years of Age (N=X)*
- Table 246:** Number and Percentage of Subjects Experiencing Unsolicited Adverse Events by MedDRA® System Organ Class and Preferred Term, Severity, Relationship, and Treatment Group – All Subjects 1273 18-55 Years of Age (N=X)*
- Table 247:** Number and Percentage of Subjects Experiencing Unsolicited Adverse Events by MedDRA® System Organ Class and Preferred Term, Severity, Relationship, and Treatment Group – 25 µg mRNA-1273 56-70 Years of Age (N=X)*
- Table 248:** Number and Percentage of Subjects Experiencing Unsolicited Adverse Events by MedDRA® System Organ Class and Preferred Term, Severity, Relationship, and Treatment Group – 50 µg mRNA-1273 56-70 Years of Age (N=X)*
- Table 249:** Number and Percentage of Subjects Experiencing Unsolicited Adverse Events by MedDRA® System Organ Class and Preferred Term, Severity, Relationship, and Treatment Group – 100 µg mRNA-1273 56-70 Years of Age (N=X)*
- Table 250:** Number and Percentage of Subjects Experiencing Unsolicited Adverse Events by MedDRA® System Organ Class and Preferred Term, Severity, Relationship, and Treatment Group – All Subjects 1273 56-70 Years of Age (N=X)*
- Table 251:** Number and Percentage of Subjects Experiencing Unsolicited Adverse Events by MedDRA® System Organ Class and Preferred Term, Severity, Relationship, and Treatment Group – 25 µg mRNA-1273 ≥71 Years of Age (N=X)*
- Table 252:** Number and Percentage of Subjects Experiencing Unsolicited Adverse Events by MedDRA® System Organ Class and Preferred Term, Severity, Relationship, and Treatment Group – 50 µg mRNA-1273 ≥71 Years of Age (N=X)*
- Table 253:** Number and Percentage of Subjects Experiencing Unsolicited Adverse Events by MedDRA® System Organ Class and Preferred Term, Severity, Relationship, and Treatment Group – 100 µg mRNA-1273 ≥71 Years of Age (N=X)*
- Table 254:** Number and Percentage of Subjects Experiencing Unsolicited Adverse Events by MedDRA® System Organ Class and Preferred Term, Severity, Relationship, and Treatment Group – All Subjects 1273 ≥71 Years of Age (N=X)*

